Tumor Tissue Genotyping for MET Gene Alteration	Testing Samples from the most recent biopsy or excision are preferred; however if no recently obtained materials are available, samples from any time during patient’s prior disease course are accepted. If study enrollment is based on Sponsor-approved local laboratory results, a tumor tissue sample for confirmatory testing by the central laboratory is expected to be available.
Circulating Tumor DNA Genotyping for MET Gene Alteration	Samples consisting of two 10 mL tubes of whole blood are collected in Streck brand Cell-Free DNA Blood Collection tubes allowing shipping and stability at ambient temperatures.
Evaluation of overall health status for future clinical trial participation	Study eligibility requires adequate performance status and organ function. Patients undertaking pre-screening for tumor /genotype with the goal of considering Study 265-109 should have health status consistent with meeting eligibility criteria in the future when they may become a candidate for the study.

Table 2: Schedule of Assessments – During Study

The Schedule of Assessments provides an overview of the protocol visits and procedures. Refer to Section 7 for detailed information on each assessment. Additional, unplanned assessments should be performed as clinically indicated, including for the purpose of fully evaluating adverse events.

Assessments	Screen/ Baseline	Cycle 1		Cycle 2		≥ Cycle 3	End of Treatment ¹⁴	
	Within 28 days	Day 1	Day 15 (± 2 days)	Day 1 (± 2 days)	Day 15 (± 2 days)	Day 1 (± 2 days)	End of Treatment/ Withdrawal	Post Treatment Follow Up
Study Participation Informed Consent ¹	Before study specific assessments							
Tumor Tissue for Genotyping ²	X							
Medical History, Disease History, Prior Therapy	X							
ECOG Performance Status	X							
Physical Exam ³	X						X	
Abbreviated Physical Exam ³		X	X	X	X	X		
Vital Signs ⁴	X	X	X	X	X	X	X	
Pregnancy Test ⁵	X	As clinically indicated						
Hematology ^{6,7}	X	X	X	X	X	X	X	
Coagulation ^{6,7}	X	As clinically indicated						
Serum Chemistry ^{6,7}	X	X	X	X	X	X	X	
PK Sampling ⁸		X	X	X	X			
PD Sampling ⁹		X	X	X	X			
ctDNA ¹⁰	X			At assessment for confirmation of disease response (PR or CR)			X	
12-Lead ECG ¹¹	X	X	X	X			X	
Disease Evaluation ¹²	X	Q 6 weeks until Week 49 (~1 year) and then Q 12 weeks						
Study Treatment Dispensing and/or Reconciliation		X		X		X		
Adverse Events ¹³ and Concomitant Medications	SAEs only	Throughout						

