7. Safety Laboratory Assessments: Hematology, coagulation, and chemistry evaluations will be performed by local laboratories.
8. PK Sampling: Samples to be taken following vital signs and electrocardiograms (ECGs). See Table 3 for details of timing related to ECGs. In the event of significant toxicities or withdrawal due to toxicity, an additional unscheduled PK blood sample should be drawn as soon as possible. In the event of a dose modification or formulation change, an additional unscheduled PK sample should be drawn at least one week after the modification or change. Each PK blood sample will consist of a 4 milliliter (mL) whole blood draw collected in one 6-mL K2EDTA tube.
9. PD Sampling: Samples to be taken as detailed in Table 3. Each PD sample will consist of whole blood draw collected in one 10-mL K2EDTA tube.
10. ctDNA: Collection of ctDNA for eligibility purposes may occur well prior to the study screening period (See Table 1). The informed consent process may be performed in accordance with documented institutional practice or using the study-specific, IRB-approved pre-screening ICF. If study enrollment is based on prospective testing by the central laboratory, an additional sample may be requested prior to dosing to ensure enough material is available for all protocol defined analyses. If study enrollment is based on Sponsor-approved local laboratory results, a ctDNA sample for retrospective confirmation by the central laboratory is expected to be available and to be collected prior to dosing. On-study samples to be taken at the time of disease assessment to confirm response (PR or CR) and at End of Treatment visit. Samples consisting of two 10mL tubes of whole blood collected in Streck brand Cell-Free DNA Blood Collection tubes allowing shipping and stability at ambient temperatures.
11. ECGs: Assessments will include an evaluation of rhythm, heart rate, and PR, QRS, QT, and QTc intervals. Single ECG to be performed at screening and at the end of treatment visit. Triplicate ECGs at Cycles 1 and 2 as described in Table 3.

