12. Disease Evaluations: To be performed at screening (28-day window allowed) and every 6 weeks from dosing date [Cycle 1, Day 1] (-7/+10 days window allowed for first on-study assessment, ± 10 days window for all other assessments) until Week 49 (~1 year) and then every 12 weeks. All on-study disease assessments should be based on a calendar schedule beginning from the first day of dosing. In general, assessments at screening/baseline as well as on-study are to include Computed Tomography (CT) scan with contrast or Magnetic Resonance Imaging (MRI) of the chest abdomen and pelvis. In addition, at screening/baseline, a MRI with and without gadolinium or CT with contrast of the brain, a whole-body bone scan and evaluation of any superficial lesions will be performed. Subsequent disease assessments should also include whole body bone scans and/or MRI of the brain if metastatic disease is identified at screening/baseline by either the **investigator OR the central radiology reviewer**. Bone scans may be performed at one-half the frequency of other radiology evaluations (every 12 weeks) and should be performed during assessment for confirmation of disease response. All scans will be sent to the central radiology reviewer. More detailed guidance on exceptional circumstances is provided in the protocol (Section 7.3).

- 13 Adverse Events: SAEs are to be reported from the time of informed consent for study participation (i.e., excluding prescreening informed consent) until resolution of all SAEs observed on study (SAEs occurring during the screening period are only reported to the safety vendor). Adverse events will be reported from the first day of study treatment until at least 28 days after last dose of study drug, and until resolution or stabilization of acute AEs and/or ongoing SAEs. Post-treatment 28-day follow-up and beyond may be performed by remote contact (e.g., telephone call).
- 14 End of Treatment: Assessments that have been completed in the previous 3 weeks do not need to be repeated (6 or 12 weeks for tumor assessments in accordance with schedule).
- 15 Long Term Follow-up: Survival status and subsequent therapies will be collected by telephone contact every 2 months (± 14 days) from end of treatment visit until death or lost to follow-up.

Table 3: Schedule of PK, Triplicate ECG, and PD Assessments

	Cycle 1, Days 1 and 15 (± 2 days Day 15 only)			Cycle 2, Days 1 or 15 (± 2 days)		

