7.5.3 Circulating Tumor DNA

Blood samples for ctDNA analysis will be collected at pre-screening or baseline, at the time of disease evaluation to confirm a disease response (PR or CR) and at the End of Treatment visit, as outlined in Table 2. For patients who are enrolled based on prospective ctDNA testing, an additional sample may be requested prior to dosing to ensure adequate amounts of blood have been received to complete the remainder of analyses required per protocol. Parameters that will be evaluated include but are not limited to *MET* mutations, *MET* gene amplification, *MET* gene rearrangement, and other genetic mutations or gene copy number changes associated with the pathogenesis of human cancers.

At each ctDNA time point, blood samples will be collected into two 10mL Streck brand Cell-Free DNA Blood Collection tubes allowing shipping and stability at ambient temperatures. For ctDNA analysis, the total volume of blood to be collected between pre-screening and End of Treatment will be up to approximately 60 mL of blood.

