Using the parameters identified, the ultimate sample size for each treatment arm is as many as 45 patients in the mITT population. The stopping rules (rejection regions), expressed as number of responses per patients treated, are 0/10, 1/14, 2/18, 3/22, 4/26, 5/29, 6/32, 7/35, 8/37, 9/39, 10/41, 11/43, 12/44, and 13/45. Thus, if more than 13 responses are observed among the first 45 patients enrolled who meet the criteria for the mITT population, the drug will be declared efficacious. If the true ORR is 20% (null hypothesis), the probability of early termination (under H_0) during the study is 0.92 and the expected sample size prior to termination is 28 patients. The Type 1 error is equal to 0.0499 and Power equal to 0.9065. If the true ORR is 40%, the probability of rejecting the hypothesis at each evaluation of the stopping rules varies, but cumulatively is 0.0935. If the true ORR is 40% and $N=45$, the exact 95% confidence interval (Clopper-Pearson) around the point estimate for ORR will be (25.7, 55.7). If the outcome in a treatment arm is promising and the option is taken to enroll up to 100 patients in the mITT in a specific treatment arm (45 patients in the initial arm plus 55 patients), to narrow the confidence interval around the ORR point estimate and to increase the size of the safety database, the exact 95% confidence interval around a true ORR of 40% will be (30.3, 50.3). Data collected in patients enrolled beyond the planned Phase 2 sample size will be used in secondary and supportive analyses. The primary analysis includes independent

evaluation of each of the four treatment arms in the first 45 patients; study expansion enables confirmation of the results of the primary analysis. The use of the Bayesian Predictive Probability Design within each arm effectively controls the overall Type I error to a maximum of 5% for each population of interest.

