9.4 Efficacy Endpoint Definitions and Analyses

9.4.1 Objective Response Rate

Objective disease response will be categorized in accordance with RECIST v1.1 (Appendix 2). Objective Response Rate (ORR) is defined as the percent of patients documented to have a confirmed Complete Response (CR) or Partial Response (PR), as reported by the central review laboratory. The primary analysis will be conducted approximately 12 weeks after the last patient is enrolled, allowing for observation of an early disease response and confirmation of PR or CR. ORR as reported by the investigator in the CRF will be used in secondary and supportive analyses as well as by the Internal Data Monitoring Committee for purpose of decision making using the Bayesian Predictive Probability Design.

Descriptive statistics (frequency and percentage) for ORR, CR, and PR will be presented. The exact 95% confidence interval of these response rates will be constructed. An exact test for single proportion (two-sided $\alpha=5\%$) will be performed to test $H_0: ORR \leq 20\%$ against $H_1: ORR > 20\%$. Other details will be described in the SAP.

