9.6.2 Gene Alterations in Tumor DNA

Tumor tissue and ctDNA genetic alterations activating *MET* will be presented descriptively, by treatment arm. Moreover, change-from-baseline in ctDNA will be presented by visit and treatment arm to assess change in genetic alteration status in ctDNA with MGCD265 treatment over time.

A concordance analysis will be conducted between target gene alterations identified in tumor tissue versus ctDNA in individual patients at prescreening/baseline. Cohen's Kappa, sensitivity and specificity will be estimated for ctDNA as well as Spearman's correlations between tumor tissue and ctDNA.

An analysis of covariance will be performed on changes in ctDNA through time including Time and Treatment as fixed effects and ctDNA at baseline as covariate.

Further details of the analyses will be presented in the SAP.

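### If Time is a visit factor in the planned ctDNA ANCOVA, its effect is confounded with initial response, because only initial responders have an on-treatment ctDNA draw

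*Combined protocol and SAP*

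**What the plan says.** Section 9.6.2 describes two analyses of ctDNA over time. The first is a descriptive table of change from baseline by visit and arm. The second is a model: "An analysis of covariance will be performed on changes in ctDNA through time including Time and Treatment as fixed effects", with baseline ctDNA as covariate. No response term, interaction or within-patient term is named, and further detail is left to the SAP.

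The sampling schedule is the same wherever it appears. Footnote 10 to Table 2 says: "On-study samples to be taken at the time of disease assessment to confirm response (PR or CR) and at End of Treatment visit". Section 7.5.3 lists a pre-screening or baseline sample and then samples "at the time of disease evaluation to confirm a disease response (PR or CR) and at the End of Treatment visit". Section 7.3 requires a confirmatory assessment, at least 4 weeks later, for patients who show a PR or CR. Section 9.2 uses observed data only, with no imputation. The objective in Section 2.1.2 concerns ctDNA alteration status over time in the selected population as a whole.

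**The concern.** The two post-baseline levels of Time do not hold the same kind of patient. The confirmation level contains only patients with an initial PR or CR. The End-of-Treatment level is open to all. Membership of the first level is fixed by outcome, by design, and not by chance dropout.

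If ctDNA changes differently in responders and non-responders, the Time effect will differ from zero even when no patient's ctDNA changes between the two visits. Baseline ctDNA does not correct this, because the imbalance lies in post-baseline change. A Time effect reported as a trend in the study population could then be partly, or wholly, a contrast of responders with everyone.

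**Working it through.** **The plan's own figures.** Inputs: the stopping boundaries 0/10, 1/14, ... 13/45 and the ORRs of 20% and 40% in Section 9.1. An exact binomial recursion through the boundaries gives, per arm:

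| True ORR | Stops before 45 | Declared efficacious | Expected N | Expected responders (95% range) |
|---|---|---|---|---|
| 20% | 0.920 | 0.0499 | 28.26 | 5.65 (0 to 14) |
| 40% | 0.069 | 0.9065 | 44.20 | 17.68 (7 to 25) |

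Section 9.1 gives 0.92, 0.0499, 0.9065 and "the expected sample size prior to termination is 28 patients" under the null, so its figures reproduce.

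**Patients with an on-treatment sample.** These are roughly the responders:
- 20% ORR: 0.20 × 28.26 = 5.7 per arm; over four arms 4 × 5.65 = 22.6 of 4 × 28.26 = 113.0 patients.
- 40% ORR: 0.40 × 44.20 = 17.7 per arm; over four arms 70.7 of 176.8.

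The counts are approximate. The draw follows an initial response, so responses that are later not confirmed add to them.

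**Bias of the Time effect.** Take Time as a two-level visit factor and assume no within-patient change between the visits. Let mean change from baseline be m_R in responders and m_N in non-responders, D = m_R − m_N, and q the non-responder share of End-of-Treatment samples.
- Confirmation level: mean m_R.
- End-of-Treatment level: mean (1 − q) m_R + q m_N.
- Difference: q (m_R − m_N) = q D.

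With an End-of-Treatment sample from every patient, q = 1 − ORR: 0.60 at 40% and 0.80 at 20%.

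**Simulation check.** The true change between visits is zero. There are 180 patients in four arms. Assumed values are between-patient SD 0.8, within-patient SD 0.6 and baseline slope −0.3. There were 300 runs, with up to 60 for the random-intercept model. Entries are mean Time estimates.

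| ORR | D | q D | Model as outlined | With patient random intercept | As outlined, plus response term |
|---|---|---|---|---|---|
| 20% | 0 | 0 | −0.018 | −0.003 | −0.010 |
| 20% | −0.5 | −0.40 | −0.374 | −0.117 | 0.007 |
| 20% | −1.0 | −0.80 | −0.779 | −0.226 | 0.005 |
| 40% | 0 | 0 | −0.006 | 0.004 | −0.002 |
| 40% | −0.5 | −0.30 | −0.293 | −0.096 | −0.002 |
| 40% | −1.0 | −0.60 | −0.587 | −0.202 | 0.000 |

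Under these SDs the outlined model rejects no Time effect at the 5% level in 53% to 54% of runs at D = −0.5, and in at least 99% at D = −1.0.

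A response term centres the estimate on zero. Without a within-patient term, however, the 5% test then rejects in only 0 to 0.3% of runs, because two samples from one patient are treated as independent. Both terms are needed.

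**Timing.** The on-treatment draw has no common date. The earliest is about 6 − 1 + 4 = 9 weeks after first dose: the first assessment at 6 weeks, its 7-day early window (Table 2, footnote 12), and 4 weeks to confirmation. Section 9.9 gives a first response at Week 19 as an example. Since Week 7 there means 6 elapsed weeks, Week 19 means 18, and confirmation falls at 18 + 4 = 22 weeks or later.

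**The case against.** The strongest reply is that the model is only outlined. Section 9.6.2 leaves detail to the SAP, and Section 9 allows the SAP to modify the protocol's plans. Whether Time is a visit factor, and whether a response or within-patient term is included, could be settled there. Section 9.6.2 also ties the over-time objective to the by-visit summary. The ANCOVA is additional, with no stated hypothesis or alpha, and D is unknown.

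Much of this stands. The by-visit table remains usable, the size of any bias cannot be fixed from the documents, and the formula applies only if Time is a visit factor. What does not stand is that deferral settles the matter. The fixed effects and covariate are already named, and followed as written they produce the confounding.

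Four stronger readings are tempting but not supported:
- A reader might take the statement that "the total volume of blood to be collected between pre-screening and End of Treatment will be up to approximately 60 mL of blood" as proof of exactly three scheduled draws. Three draws of two 10 mL tubes do make 60 mL. But Section 7.5.3 also allows an extra pre-dose sample, so baseline, extra and End-of-Treatment samples give the same total. The schedule itself carries the point.
- A reader might infer from "The primary analysis will be conducted approximately 12 weeks after the last patient is enrolled" that many responders would lack an End-of-Treatment sample, which would raise q. That sentence times the ORR analysis, not the ctDNA analysis, and non-responders with stable disease may also still be on treatment. As pure assumption at 40% ORR, losing half the responders' samples gives q = 0.6/(0.2 + 0.6) = 0.75. Losing a quarter of the non-responders' samples as well gives 0.45/(0.2 + 0.45) = 0.69.
- A reader might suppose that a random patient intercept cures the problem. In the simulation it reduces the bias but does not remove it.
- A reader might conclude that the trial's efficacy inference is affected. It is not: no decision rule uses ctDNA change.

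**Conclusion.** The concern holds in a limited form. If Time is a visit factor, the outlined ANCOVA confounds it with initial response. With complete End-of-Treatment samples and no within-patient change between visits, the spurious effect is 0.60 D at 40% ORR and 0.80 D at 20% ORR. It is zero if responders and non-responders do not differ in ctDNA change. D and the SDs are assumptions. The schedule and the outlined model come from the documents.

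No model can recover on-treatment change in non-responders, who have no scheduled on-treatment sample. It would go too far to conclude that the over-time objective fails. Baseline-to-End-of-Treatment change covers all patients with that sample, and the by-visit table can be read correctly once labelled. Severity is minor: this is one secondary biomarker analysis, and the primary endpoint, stopping rules and sample size are unaffected.

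**What to change.** In Section 9.6.2 or the SAP:
1. State whether Time is a visit factor or elapsed time, and that the pooled Time effect will not be interpreted as a population trend.
2. Either restrict the confirmation versus End-of-Treatment contrast to initial responders, or add an initial-response term together with a within-patient term. In both cases say that the contrast describes responders only.
3. Report baseline-to-End-of-Treatment change in all patients with that sample as the population estimate, with the number lacking one.
4. Label the confirmation column of the by-visit summary as patients with an initial response only, and show the actual sampling week.

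The cost is wording and a small change to the analysis, with no new samples or visits. The price is a narrower claim for one secondary objective.

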9.1 Hypothesis and Sample Size

This Phase 2, parallel-arm study will use a Bayesian Predictive Probability Design (Lee-2008) that minimizes the number of patients enrolled to test the hypothesis. The design will be applied separately and using the same assumptions in each of four treatment arms. As many as 45 patients are planned for inclusion in the primary analysis for each treatment arm. The study also provides for the addition of up to 55 patients to each of two treatment arms to provide sufficient safety and/or efficacy data to support an accelerated approval market application in two study populations. Thus, the ultimate sample size for this study could include as many as 290 patients.

ORR in accordance with RECIST v1.1 is the primary endpoint. With currently available treatments, ORR is assumed to be 20% (p_0), thus this rate is considered uninteresting. The target ORR using MGCD265 in this study is 40% (p_1). The trial will monitor the number of observed responses continuously after evaluating the first on-study disease assessments of the first 10 patients in each treatment arm in the mITT population. In creating the statistical design, the Type 1 error (α) is constrained to < 0.05 and Power ($1-\beta$) is constrained to ≥ 0.90 .

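### The ctDNA ANCOVA in Section 9.6.2 names no within-patient covariance, although responders can give two scheduled post-baseline samples

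*Combined protocol and SAP*

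**What the plan says.** Section 9.6.2 presents ctDNA change from baseline by visit and arm and then adds one inferential model, an analysis of covariance "performed on changes in ctDNA through time including Time and Treatment as fixed effects and ctDNA at baseline as covariate". No patient term, repeated-measures statement or covariance structure is given. The section closes with "Further details of the analyses will be presented in the SAP". The supplied document contains no further SAP text on this model.

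The sampling schedule is in Table 2, footnote 10: "On-study samples to be taken at the time of disease assessment to confirm response (PR or CR) and at End of Treatment visit". Section 7.5.3 repeats it and states that "the total volume of blood to be collected between pre-screening and End of Treatment will be up to approximately 60 mL of blood".

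Change in ctDNA over time is a secondary objective (Section 2.1.2) and a secondary endpoint (Section 2.2.2). The objective concerns the selected population as a whole. No hypothesis comparing arms on ctDNA is stated.

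**The concern.** Time is a factor in the model, so all post-baseline values enter one fit. Responders can contribute two changes, both measured from the same baseline value. Other patients contribute at most one. Adjusting for baseline does not remove the correlation left between two values from one patient.

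An ordinary ANCOVA assumes independent residuals. With any positive within-patient correlation, that assumption understates the variance of an arm mean and overstates the variance of the contrast between confirmation and End of Treatment. The first makes arm comparisons anti-conservative. The second costs power on the Time effect, which is closer to the stated objective.

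What is at stake is the reliability of the only inferential model named for this secondary endpoint.

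**Working it through.** **No figure to reproduce.** The plan gives no alpha, power or sample size for this model. The ORR operating characteristics in Section 9.1 do reproduce by exact recursion over the listed boundaries (Type 1 error 0.0499, power 0.9065, early termination 0.92, expected sample size 28.3 against a stated 28), but they concern a different analysis.

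**Number of samples.** Each draw is two 10 mL tubes. The stated 60 mL is 3 × 2 × 10 mL: one baseline draw and at most two later ones. The second later draw exists only for responders.

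**Inputs**
- Arms: 4, so the overall arm test has 3 df (Section 9.1).
- Patients per arm: 45 (Section 9.1).
- Share *f* with two post-baseline samples: 0.20 and 0.40. These are the uninteresting and target ORR of Section 9.1, used here as a proxy.
- Within-patient correlation ρ: not stated; assumed 0.3 to 0.8.
- Nominal alpha: not stated for this model; assumed 0.05 two-sided. Section 9.4.1 sets 5% for the ORR test only.
- Equal variances, the same *f* in each arm, and an End of Treatment sample from every patient: assumed.

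**Arm comparison.** The variance of an arm mean is understated by the factor

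D = [(1 − f) + 2f(1 + ρ)] / (1 + f).

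For f = 0.40 and 45 patients (27 with one value, 18 with two) and ρ = 0.5: D = (27 + 36 × 1.5)/63 = 81/63 = 1.286.

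The actual error is 2[1 − Φ(1.96/√D)] for a pairwise contrast and P(χ²₃ > 7.815/D) for the 3-df test. The simulated columns come from 4,000 trials per row (4 × 45 patients, no true arm or Time effect, least squares on Time, arm and baseline).

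| f | ρ | D | Pairwise, formula | Pairwise, simulated | 3-df, formula | 3-df, simulated |
|---|---|---|---|---|---|---|
| 0.20 | 0.3 | 1.100 | 0.062 | 0.063 | 0.069 | 0.068 |
| 0.20 | 0.5 | 1.167 | 0.070 | 0.069 | 0.082 | 0.087 |
| 0.20 | 0.8 | 1.267 | 0.082 | 0.093 | 0.104 | 0.105 |
| 0.40 | 0.3 | 1.171 | 0.070 | 0.071 | 0.083 | 0.081 |
| 0.40 | 0.5 | 1.286 | 0.084 | 0.080 | 0.108 | 0.099 |
| 0.40 | 0.8 | 1.457 | 0.104 | 0.106 | 0.147 | 0.152 |

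D does not depend on arm size, which matters because arms may stop early. With 15 patients per arm, f = 0.40 and ρ = 0.5, the simulated rates are 0.078 (pairwise) and 0.108 (3-df).

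**Time contrast.** With N patients, of whom fN have a confirmation sample, the ordinary model takes the variance of the difference between the two time means as proportional to 1/f + 1. The true value is 1/f + 1 − 2ρ. At ρ = 0.5:
- f = 0.40: ratio 2.5/3.5 = 0.714, so the actual error is 2[1 − Φ(1.96/√0.714)] = 0.020.
- f = 0.20: ratio 5/6 = 0.833, so the actual error is 0.032.

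**With a within-patient covariance.** Generalised least squares with a compound-symmetric covariance, in the same simulations, brings the 3-df arm test to between 4.2% and 5.1%. That run used the true correlation; in practice it would be estimated.

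**The case against.** The strongest reply is that the text does not say samples are treated as independent. A marginal repeated-measures model with unstructured covariance also lists only fixed effects, and covariance structure is the kind of detail that Section 9.6.2 leaves to the SAP. This stands against any claim that the plan commits to independence. It does not dispose of the point. The protocol has already named the model class, the effects and the covariate, and the one element that repeated sampling requires is absent.

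Second, no arm hypothesis or decision rule uses this model. All arms receive the same drug, the objective is change over time, and a descriptive presentation by visit and arm is planned as well. This also stands, and it limits the consequence. A reader might infer that the tests behind the secondary objective are both invalid; the documents do not support that.

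Third, the inputs may be too high. The two samples are taken at response and at End of Treatment, often at progression, so the correlation could be low. At ρ = 0.1 and f = 0.40, D = (0.6 + 0.8 × 1.1)/1.4 = 1.057 and the 3-df error is 0.060. The primary analysis falls about 12 weeks after the last enrolment (Section 9.4.1). If ctDNA is analysed then, responders still on treatment would have only one post-baseline value. Both remarks reduce the size and leave the direction unchanged for any positive correlation.

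Fourth, the confirmation sample exists only for responders, so Time is confounded with response whatever the covariance. This is correct, and the proposed change does not cure it. The Time error rates above also assume no such effect.

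**Conclusion.** The point holds as an omission in the named model. Read literally as an ordinary ANCOVA, it is anti-conservative for arms and conservative for Time. Under the stated assumptions (alpha 0.05, 20% to 40% of patients with two samples, correlation 0.3 to 0.8) the arm error is about 0.06 to 0.10 pairwise and 0.07 to 0.15 on 3 df, which is about 1.2 to 2.9 times nominal. The Time contrast at correlation 0.5 rejects about 0.02 to 0.03. Fewer patients with two samples would mean less inflation.

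A reader might infer that the arm error is about twice nominal. The documents do not support one such figure. A doubled 3-df rate needs a correlation of about 0.44 at a 40% share or 0.75 at 20%. A doubled pairwise rate needs about 0.73 at 40% and cannot occur at 20%, where even perfect correlation gives 0.090.

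The primary ORR inference is not affected.

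**What to change.** In Section 9.6.2 or in the SAP, replace the ANCOVA with a linear repeated-measures model for ctDNA change. Keep Time, arm and baseline ctDNA as they are, add a patient random intercept or an unstructured within-patient covariance, and use Kenward-Roger degrees of freedom. State also that the Time effect is to be interpreted as confounded with response, because the confirmation sample is triggered by response.

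The cost is one or two sentences, with no new samples or visits. Section 9 already allows the SAP to modify the protocol's plans and requires a protocol amendment only for major changes to the primary endpoint or its analysis.
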